4.2.2.3 Symptomatic COVID-19

Symptomatic COVID-19 is defined as laboratory-confirmed SARS-CoV-2 infection accompanied by protocol-defined COVID-19-like illness.

The start date of the illness episode is the first date of the first symptom onset corresponding to a single CLI. The stop date is the last day of the last symptom, provided that such date is followed by an asymptomatic period of at least 3 days; if symptoms reoccur earlier than the completion of the 3-day asymptomatic period, then the reoccurring symptoms are to be considered part of the same illness rather than a new illness. If symptoms reoccur after an asymptomatic period of at least 3 days, then those symptoms are to be considered a new CLI.

Exacerbation/worsening of symptoms can also be indicative of a new CLI. In the event of an illness with a positive NAAT for SARS-CoV-2, exacerbation/worsening of CLI symptoms or occurrence of new symptoms during the ongoing illness will be considered part of the ongoing COVID-19 illness episode.

In the event of exacerbation/worsening of CLI symptoms or occurrences of new symptoms during an ongoing illness which is not associated with a positive NAAT for SARS-CoV-2 (missing or

negative test), investigator judgement will determine if the new symptom(s) or/and the worsening of the symptom(s) suggest the possibility of a new illness that merits triggering a new illness form creation and new collection of respiratory samples and other illness related study procedures. In such cases, the onset of illness will correspond to the date of onset of the new symptom(s) or the date of the worsening of the pre-existing symptom(s).

In these instances of overlapping CLIs, the start date of the new CLI will be the date of exacerbation / worsening as collected in the CRF. The stop date of the 1st CLI will be the same as the stop date of the new CLI (following the rule stated above).

All information will be based on symptoms/features collected in the CRF corresponding to the same episode.

The derivation criteria for symptomatic COVID-19 is as follows:

- A CLI is identified in the CRF, the corresponding nasopharyngeal swab sample is collected during the CLI episode and the nasopharyngeal sample shows a positive result in the protocol-defined NAAT.
- A CLI is identified in the CRF, the CLI time of onset date is within the 7 days from the last vaccination dates (eg. D01 is visit 1, 7 days gives the range of D01 to D08) and the corresponding swab sample collected from the last visit or during the CLI shows a positive result from the protocol-defined NAAT.
- A CLI is identified, a positive COVID-19 local NAAT test result is recorded in CRF and the sample collection date for local test is within the range of [start date – 2 days, stop date] of a CLI for the participant.

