4.2.2 Other Safety Endpoints

For the safety endpoint related to SARS-CoV-2 infections (endpoints from [Section 4.2.2.1](#) to [Section 4.2.2.7](#)), main analysis will be applied including only those cases with start date before a participant received a non-study authorized/approved COVID-19 vaccine if applicable. Other cases with start date reported in participants after the receipt of an authorized/approved COVID-19 vaccine will be listed separately.

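### With overlapping illnesses, one positive local NAAT in the second also makes the first symptomatic COVID-19, which duplicates the episode and gives it an earlier onset

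*SAP*

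**What the plan says.** Section 4.2.2.3 of the SAP treats worsening during an ongoing illness in two ways. If the illness already has a positive NAAT, the worsening belongs to the same COVID-19 episode. If the NAAT is missing or negative, the investigator may judge that a new illness is possible and open a second CLI. In that overlapping case, "the start date of the new CLI will be the date of exacerbation / worsening as collected in the CRF", and "The stop date of the 1st CLI will be the same as the stop date of the new CLI".

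The same section gives three routes to symptomatic COVID-19. The two based on the protocol-defined NAAT refer to the swab that belongs to the illness; the first, for example, asks that "the corresponding nasopharyngeal swab sample is collected during the CLI episode". The third route, for local tests, requires only a positive result where "the sample collection date for local test is within the range of [start date – 2 days, stop date] of a CLI for the participant". It has no comparable link between sample and illness.

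Section 4.2.2 decides which cases count by their start date: the main analysis is applied "including only those cases with start date before a participant received a non-study authorized/approved COVID-19 vaccine", and later cases are listed separately. Section 3.4.5 summarises symptomatic COVID-19 as a percentage of participants, and gives only a listing when fewer than 5 cases are observed. Section 4.2.2.6 gives severe COVID-19 the start and stop dates of the symptomatic episode to which it belongs.

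**The concern.** The SAP separates the two illnesses because the first was not NAAT-positive. It then lets the second illness's test classify the first as COVID-19. No rule merges overlapping CLIs, removes duplicates or assigns a positive local test to one of them.

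Three outputs are at stake. One infection can appear as two symptomatic COVID-19 episodes. The extra episode carries the onset of the first illness, and a severe case attached to that episode takes the same date. Because the start date decides on which side of a non-study vaccination a case falls, the earlier onset can also move a participant into the main analysis when the test-positive illness began after that vaccination.

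**Working it through.** The SAP states no figure on this point, so the check applies its date rules literally.

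**General result.** Let the first CLI start on day s1 and the second on day s2, with s1 < s2, and let the second stop on day e. Under section 4.2.2.3 the first CLI also stops on day e. The local-test windows are:

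- first CLI: [s1 − 2, e]
- second CLI: [s2 − 2, e]

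Since s1 − 2 < s2 − 2 and the right-hand ends are equal, the second window lies wholly inside the first. Any local sample that qualifies the second CLI also qualifies the first, whatever the dates.

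**Example (dates assumed for illustration).** The first CLI starts on day 100 with a negative swab. Worsening on day 110 opens the second CLI. The last symptom is on day 120, a local NAAT is positive on day 111, and a non-study vaccine is given on day 105.

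| | First CLI | Second CLI |
|---|---|---|
| Window | [100 − 2, 120] = [98, 120] | [110 − 2, 120] = [108, 120] |
| Contains day 111? | yes | yes |
| Derived as symptomatic COVID-19? | yes, onset day 100 | yes, onset day 110 |
| Start before the day-105 vaccine? | yes: main analysis | no: listed separately |

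The second window has 120 − 108 + 1 = 13 days, and all 13 also lie in the first window.

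**Effect on each output.**

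- *Episodes.* One positive test gives 2 episodes. The extra onset is 110 − 100 = 10 days earlier.
- *Fewer-than-5 rule.* If cases are counted as derived episodes, three such participants with no non-study vaccine give 3 × 2 = 6 cases instead of 3, which crosses the threshold.
- *Percentage of participants.* Each participant counts once, so two episodes on the same side of the cut-off change nothing. With the vaccine on day X, the numerator changes only if s1 < X ≤ s2. The participant then contributes 1 to the main analysis instead of 0, provided there is no other qualifying case. At the planned Comparator Group size of 515, one such participant moves the percentage by 1/515 = 0.19 percentage points.

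**The same example with one test linked to one CLI (rule given under the fix).** A sample on days 110 to 120 (11 days) goes to the second CLI: one case, onset day 110, listed separately. A sample on day 108 or 109 was taken while only the first CLI was under way, so it goes to the first. That illness is then NAAT-positive and the worsening on day 110 is part of it: one case, onset day 100. All 13 sample days give exactly one case.

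**The case against.** The best defence has four parts.

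First, the stated summary is a percentage of participants, so a duplicated episode does not count anyone twice. This stands. A reader might infer that the reported COVID-19 percentages are inflated in general, or doubled for such participants. Section 3.4.5 does not support that: outside the cut-off situation the percentage is unchanged.

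Second, the first illness may truly have been COVID-19. Its NAAT may be missing rather than negative, and a second form needs only the investigator's view that a new illness is possible. With continuous symptoms and no test, the earlier onset is plausible. This also stands, so the first episode cannot be called false in every case. But the SAP should settle the matter by an explicit rule, and at present the stop-date convention settles it as a side effect.

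Third, the extended stop date is consistent with the SAP's requirement of at least 3 symptom-free days before an illness closes. That justifies the date for describing symptom duration. It does not justify using it as a test window for an illness that was deliberately kept separate.

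Fourth, the reach is narrow. The two criteria based on the protocol-defined NAAT refer to the corresponding swab, which can be read as preventing the problem there. Nor do severity signs recorded under the second illness pass automatically to the first, because section 4.2.2.3 ties information to symptoms and features of the same episode. A reader might also infer that hospitalised COVID-19 is misdated. It is not: section 4.2.2.5 gives it its own admission and discharge dates, and only its status as an episode depends on this derivation.

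Two sentences in section 4.2.2.3 might seem to resolve the matter. The rule that worsening belongs to an ongoing NAAT-positive illness covers the opposite situation, and applied backwards it would keep the earlier onset. The sentence on information from the same episode concerns symptoms and features and does not assign tests.

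**Conclusion.** The point holds as a derivation error for local NAAT results. For every overlapping pair with a positive local test in the second CLI's window, the text as written yields two symptomatic COVID-19 episodes, and this does not depend on the dates chosen. The duplication reaches episode counts, listings and the fewer-than-5-cases rule, and it misdates severe COVID-19 if that is attached to the first CLI. The percentage of participants is affected only when a non-study vaccine falls between the two onsets. Section 4.2.1 itself expects non-study vaccination to be likely in the Comparator Group, so that situation is possible there.

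The SAP does not say how many such pairs to expect. The number is probably small, since it takes an overlap, no positive NAAT in the first illness, an investigator's decision to open a second, and a positive local test. The endpoint is descriptive secondary safety, with no hypothesis test attached. The correction is worth making because the rule gives a wrong result as written and costs little to repair. No primary conclusion depends on it.

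**What to change.** Add a linkage rule to section 4.2.2.3:

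- Link each positive local NAAT to one CLI only: among the CLIs under way on the sample date, the one with the latest start date on or before that date.
- Use the 2-day window before onset only when the sample falls in no CLI already under way.
- If the sample predates the worsening, treat the worsening as part of the ongoing NAAT-positive episode, as the section already provides.
- Keep the extended stop date of the first CLI for symptom duration only.

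Two simpler repairs fall short. Closing the first CLI on the day before the second starts gives windows [98, 109] and [108, 120] in the example, so days 108 and 109 still qualify both. Linking the test to the latest CLI that starts on or before sample date + 2 days gives a unique link, but it moves a positive sample taken during the first illness (day 108 or 109) to the second, against the ongoing-episode rule.

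If the sponsor wants the earlier onset when the first NAAT is missing, the SAP should say so as a stated exception. The cost is a few sentences and a small change to the derivation code, with no new data. It should be settled before the next database lock.

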All Supplemental Cohort participants will be followed for the duration of the study to capture occurrences of COVID-19 through passive surveillance wherein participants will be instructed to contact the site if they experience symptoms/conditions of a COVID-19-like illness at any time during the study. In addition, active surveillance will be undertaken in all participants wherein all participants will be contacted once every 2 weeks starting after the last injection to enquire about development of COVID-19-like illness.

The duration of participation in the study for each participant will be:

- Supplemental Cohorts 1 and 2: approximately 365 days post-booster injection (ie, approximately 366 days total)
- Supplemental Cohorts Comparator Groups: approximately 365 days post-injection 2 (ie, approximately 386 days total)

2 Objectives and Endpoints

Table 2.1: Objectives and endpoints

Primary Safety	
To assess the safety profile of all participants in each age group and in each study Intervention Group.	
 • Presence of unsolicited systemic AEs reported in the 30 minutes after each vaccination • Presence of solicited (pre-listed in the participant's diary card [DC] and [electronic] Case Report Form [CRF]) injection site reactions and systemic reactions occurring up to 7 days after each vaccination • Presence of unsolicited AEs reported up to 21 days after the last vaccination • Presence of serious adverse events (SAEs) throughout the study • Presence of AESIs throughout the study • Presence of MAAEs throughout the study
Primary Immunogenicity-Supplemental Cohort 1	

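### The derivation of symptomatic COVID-19 accepts no swab taken after the last symptom day, so an illness whose only positive swab came later is not counted, even if the swab was collected for that illness

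*SAP*

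**What the plan says.** All references are to the SAP.

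The endpoint is defined in section 4.2.2.3: "Symptomatic COVID-19 is defined as laboratory-confirmed SARS-CoV-2 infection accompanied by protocol-defined COVID-19-like illness". No day window is attached to this sentence. Laboratory confirmation (section 4.2.2.1) needs one positive NAAT, central or local, on any respiratory sample taken during the study.

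The same section fixes the limits of an episode. For the start: "The start date of the illness episode is the first date of the first symptom onset corresponding to a single CLI". For the end (the closing figure is in days): "The stop date is the last day of the last symptom, provided that such date is followed by an asymptomatic period of at least 3".

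Three derivation criteria follow:

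1. A CLI is in the CRF, "the corresponding nasopharyngeal swab sample is collected during the CLI episode", and the protocol-defined NAAT is positive.
2. The CLI begins within 7 days of the last vaccination, and "the corresponding swab sample collected from the last visit or during the CLI shows a positive result from the protocol-defined NAAT".
3. A local NAAT is positive, and "the sample collection date for local test is within the range of [start date – 2 days, stop date] of a CLI".

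Sections 4.2.2.5 and 4.2.2.6 build hospitalized and severe COVID-19 on symptomatic COVID-19. Section 1 describes surveillance. Participants are told to report symptoms to the site whenever they occur, and in addition "all participants will be contacted once every 2 weeks starting after the last injection to enquire about development of COVID-19-like illness".

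**The concern.** The definition asks that infection and illness go together. The derivation asks that the swab be dated no later than the last day of symptoms. A participant who recovers quickly, or is seen a few days after reporting, can have a positive swab taken to investigate that very illness and still not be a case.

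The section itself recognises that test and symptom dates need not coincide. It allows local tests 2 days before onset, and it allows the last-visit swab when onset is soon after vaccination. It makes no allowance at the other end. Even a swab taken in the 3 symptom-free days needed to confirm the stop date lies outside the episode if symptoms do not return.

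At stake is the count for a secondary safety endpoint and for the two endpoints built on it. Whether a case is lost depends on symptom duration and on how fast the participant is seen, not on whether the infection was symptomatic. Section 3.4.5 replaces the summary by a listing when fewer than 5 COVID-19 illness cases are observed, so a small undercount could also change what is tabulated.

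**Working it through.** The SAP gives no event count, sample size or power for this endpoint, so there is no figure to reproduce. The check is first a reading of the rules, then an illustrative count.

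**Reading the rules.** Take symptoms on days 1 and 2 and a positive protocol-defined NAAT on day 4, more than 7 days after any vaccination and with no local test. Suppose that the illness qualifies as a CLI and that a swab is taken at that point; both depend on the protocol.

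- Criterion 1: start = day 1, stop = day 2, swab = day 4 > day 2. Not met.
- Criterion 2: onset is outside the 7 days. Not met. With onset inside the 7 days, a day-4 swab would still be after the CLI; only a positive last-visit swab would rescue the case.
- Criterion 3: no local test. A local test on day 4 would also fail, because its window ends on day 2.
- Section 4.2.2.1: one positive NAAT during the study. Met.

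The participant is a laboratory-confirmed infection but not a symptomatic case. A swab on day 2 would have met criterion 1, so the limit is the last symptom day inclusive.

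**Illustrative count.** Let D be the number of symptom days, w the days from onset until the site learns of the illness, and s the further days to the swab. The swab falls on symptom day w + s + 1, so it counts if w + s ≤ D − 1. From the SAP: the 14-day contact interval. Assumed: D, s, w uniform on 0 to 13 for illnesses found only at the contact, no positive local test, and a swab still taken and still positive after symptoms end.

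For illnesses found only at the contact, D − s of the 14 values of w qualify (for s ≤ D ≤ 14 + s), so the share lost is 1 − (D − s)/14. Example: D = 7, s = 2 gives 1 − 5/14 = 64%.

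For illnesses reported on symptom day 1 (w = 0), the case is lost only if s > D − 1. With 80% so reported and s = 2, none of that 80% is lost when D ≥ 3, and the overall share is 0.2 × [1 − (D − 2)/14]. Example: D = 7 gives 0.2 × 0.643 = 13%.

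| D (days) | Contact only, s = 0 | Contact only, s = 2 | 80% self-reported on day 1, s = 2 |
|---|---|---|---|
| 3 | 79% | 93% | 19% |
| 5 | 64% | 79% | 16% |
| 7 | 50% | 64% | 13% |
| 10 | 29% | 43% | 9% |
| 14 | 0% | 14% | 3% |

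For D = 2 and s = 2 the share is 100% however the illness is found, because 2 > D − 1 = 1.

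**The case against.** **The central swab may already be linked through the CRF.** Criterion 1 speaks of the swab corresponding to the CLI and, unlike criterion 3, sets no numeric date bounds. This shows that the wording could be clearer. It does not remove the limit, because collection during the episode is a separate condition next to the link, and the section defines when the episode ends.

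**A time link is legitimate.** Infection accompanied by illness implies some closeness in time, and asking for a swab during symptoms favours specificity. This stands: having a window is no error. What is open to criticism is closing it on the last symptom day even for the swab taken for that illness.

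**The cases do not vanish.** They remain laboratory-confirmed infections under section 4.2.2.1. This also stands; only the symptomatic label, and what is built on it, is lost.

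**The size rests on assumptions.** This stands in full. CLI visit timing is not in the SAP text, and the SAP does not say whether a swab is taken once symptoms are over. If none is taken, the rule loses nothing.

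**Stronger readings that are not supported.** A reader might infer that short illnesses, or all illnesses found at the two-weekly contact, are dropped as a class. They are not: an illness still present at the swab, or with a positive local test in its window, is counted, and self-reporting runs in parallel with the contact. Nor is the upper limit peculiar to the central laboratory, since the local window also ends at the stop date. Differential loss between groups is conceivable because Cohort 1 and the Comparator Group are open-label, but nothing in the SAP shows it.

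**Conclusion.** The point holds for one defined set of cases: illnesses whose only positive NAAT is dated after the last symptom day, apart from those that a positive last-visit swab brings in under criterion 2. They match the wording of the definition but not the derivation, and hospitalized and severe COVID-19 inherit the gap.

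The size cannot be settled from the SAP. The table shows that it runs from negligible to large, driven by illness duration, swab delay and the share of illnesses that participants report themselves. The high figures apply only to illnesses found solely at the contact. The endpoint is secondary and described by percentages with Clopper-Pearson intervals, so no hypothesis test, alpha level or power is touched. This is a minor but worthwhile correction.

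**What to change.** - In criterion 1, accept a positive protocol-defined NAAT on the swab collected at the CLI visit recorded for that episode, whether or not symptoms had stopped.
- Assign each positive swab to one episode only, namely the CLI for which it was collected.
- If local tests are also given an allowance after the stop date, end it before the start of any new CLI. A fixed allowance alone would not do: symptoms returning after 3 symptom-free days open a new CLI, so with 7 days allowed, a swab on stop + 5 could confirm both the first CLI and one starting on stop + 4.
- List the cases that qualify only through the extension, and give the count with and without them.

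The cost is a line or two of SAP wording and a small change to one derivation. The downside is that a few late positives from another infection may be attributed to the illness; the listing and the paired counts keep that visible.

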4.2.2.4 SARS-CoV-2 Infection

SARS-CoV-2 infection is defined as a serologically-confirmed SARS-CoV-2 infection OR laboratory-confirmed SARS-CoV-2 infection.

4.2.2.5 Hospitalized COVID-19

Hospitalized COVID-19 is defined as an episode of symptomatic COVID-19 that requires inpatient hospitalization.

The start date of hospitalization is the date when the participant is admitted to a hospital as collected in CRF. The stop date of hospitalization is the participant's discharge date from the hospital as collected in CRF.

4.2.2.6 Severe COVID-19

Severe COVID-19 is defined as symptomatic COVID-19 with any one of the following:

- Any clinical signs of severe illness measured at least on 2 occasions separated by 30 minutes (saturation of oxygen [SpO_2] \leq 93% on room air (corrected for altitude), $\text{PaO}_2/\text{FiO}_2 < 300$ mm Hg, respiratory rate \geq 30 breaths per minute at rest, heart rate \geq 125 beats per minute at rest)

- Supplemental oxygen administration for > 1 hour
- Use of invasive or non-invasive ventilation or Extracorporeal Membrane Oxygenation
- Clinical diagnosis of respiratory failure (ie, clinical need for one of the preceding therapies, but preceding therapies not able to be administered in setting of resource limitation)
- Significant acute renal, hepatic, or neurologic dysfunction
- Shock (defined by systolic blood pressure < 90 mm Hg, or diastolic blood pressure < 60 mm Hg or requiring vasopressors)
- Admission to an ICU
- Death

This endpoint is analyzed as data collected in CRF. The start date and stop date is the same than that of the corresponding symptomatic COVID-19.

